**Title:** Diagnostic Accuracy of Artificial Intelligence, CBCT, and Clinical Examination in Detecting Number of Root Canals in Conventional and Retreated Maxillary and Mandibular Molars

NCT Number: "Pending"

Date: 29/10/2024

Introduction: Accurate root canal detection is crucial for successful endodontic treatment, particularly in complex molar cases. Conventional methods, such as clinical examination and cone-beam computed tomography (CBCT), have their limitations, as high radiation exposure. Recent advancements in Artificial Intelligence (AI) have shown promise in improving diagnostic accuracy. This study aims to compare the effectiveness of AI, CBCT, and clinical examination using a dental operating microscope (DOM) in detecting root canals in upper first, upper second, and lower first molars, in both conventional and retreatment cases.

Methods: CBCT scans from 210 patients requiring non-surgical root canal therapy or re-treatment were selected. The scans were analyzed using three detection methods: clinical examination via DOM, interpretation by two experienced endodontists using CBCT, and an AI convolutional neural network (CNN) software (Diagnocat). The detected number of root canals was recorded and compared across the three methods. Statistical analysis was performed to evaluate the diagnostic accuracy, including sensitivity, specificity, and agreement between methods.

Results: AI detected a significantly higher number of molars with three or four canals compared to clinical examination and CBCT in conventional treatment cases (P < 0.001). In retreatment cases, AI demonstrated a similar trend, with one case of five root canals detected clinically but missed by both CBCT and AI. Overall, AI showed higher diagnostic accuracy (88.2%) compared to clinical examination and CBCT. There was no significant difference in AI accuracy between molar types, though the upper first molar had the highest accuracy (93.9%).

Conclusion: AI demonstrated higher accuracy in detecting root canals compared to CBCT and clinical examination in both conventional and retreatment cases, particularly in upper molars. These findings highlight the potential of AI as a valuable tool for enhancing diagnostic precision in endodontics, especially in complex cases. However, further research is necessary to address the limitations of AI

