## **Study Design**

- Sample Size: 212 molars.
- Randomization: Not applicable (observational study).
- **Blinding**: Independent assessment by two experienced endodontists for CBCT and clinical examination.
- Control Group: Not applicable.

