#### **Statistical Analysis Plan**

- Descriptive analysis of frequencies and percentages.
- Friedman's test for comparison between methods.
- Kappa statistics for agreement between methods.
- ROC curve analysis to determine diagnostic accuracy measures (AUC comparison).

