Title: Diagnostic Accuracy of Artificial Intelligence, CBCT, and Clinical Examination in Detecting Number of Root Canals in Conventional and Retreated Maxillary and Mandibular Molars

NCT Number: “Pending”

Date: 29/10/2024

Statistical Analysis

Qualitative data were presented as frequencies and percentages. Friedman's test was used to compare between number of canals detected by the three methods. Kappastatistic was used to assess agreement between the threemethods. Kappa values ranging from 0.6 to 0.8 indicate good agreement while values ranging from 0.8 to 0.99 indicate very good agreement. Numerical data were explored for normality by checking the distribution of data and using tests of normality (Kolmogorov-Smirnov and Shapiro-Wilk tests). All data showed normal (parametric) distribution except for length of canal division from the apex and percentage of canal unity data which showed non-normal (non-parametric) distribution. Data were presented as mean, standard deviation (SD), median and range values. For parametric data, Student's t-test was used to compare between correctly and incorrectly diagnosedcases. For non-parametric data, MannWhitney U was used to compare between correctly and incorrectly diagnosed cases. Binary logistic regression model was constructed using diagnosis (Correct/Incorrect) as the dependent variable. Treatment, molar type, inter-orifice distance, percentage of canal unity and Vertucci classification were the independent variables. The significance level was set at $P \leq 0.05$. Statistical analysis was performed with IBM SPSS Statistics for Windows, Version 23.0. Armonk, NY: IBM Corp. ROC (Receiver Operating Characteristic) curve was constructed to determine the diagnostic accuracy measures of AI in relation to CBCT. Comparison between areas under the ROC curve (AUC) were performed using z-test. ROC curve analysis was performed with MedCalc® Statistical Software version 19.5.1 (MedCalc Software Ltd, Ostend, Belgium; <https://www.medcalc.org>; 2020)

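### The claim that AI exceeds both comparators on molars with three or four canals has no listed pairwise test behind it; Friedman's test is omnibus and does not test that combined count

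*Protocol*

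**What the plan says.** The Results part of the protocol's abstract reports that "AI detected a significantly higher number of molars with three or four canals compared to clinical examination and CBCT". The P value beside this statement is below 0.001 and refers to the conventionally treated subgroup. The abstract gives no separate counts for three and four canals, no size for that subgroup and no name for the test.

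The Methods part of the same abstract says what was measured: "The detected number of root canals was recorded and compared across the three methods". The finer data therefore exist.

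For the comparison across methods, the protocol's Statistical Analysis Plan section lists "Friedman's test for comparison between methods", and the SAP says "Friedman's test was used to compare between number of canals detected by the three methods". Kappa and ROC analyses are also planned, for agreement and for accuracy measures. Neither document lists a test of a category count, a post-hoc pairwise test on canal number, or a multiplicity rule. The SAP's significance level is 0.05.

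**The concern.** The sentence makes three claims at once: a higher count in a combined category, a difference from each of two comparators, and a direction favouring AI. It is the only significant difference that the abstract reports.

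Two things do not fit. First, a tooth read as three instead of four stays inside the combined category, so the count quoted cannot show that error. With the number of molars fixed, a higher combined count only means fewer readings of two or below, or of five. Second, the one listed test that compares canal number across the three methods asks whether the methods' within-tooth ranks differ somewhere. That is a different hypothesis from equal category counts. It also does not say which methods differ, or which way.

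At stake is whether the reported P value can be cited as evidence that AI differs from CBCT and from the microscope, and in AI's favour.

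**Working it through.** **The plan's own figure.** P < 0.001 cannot be reproduced. The documents give no canal counts per method, no paired cross-table and no subgroup size. What can be checked is whether Friedman's test, if it is the source, could support the sentence. All counts below are assumptions, not trial data. I take n = 106, half of the 212 molars in the protocol's Study Design section. Teeth on which all methods agree drop out of the statistic, so this choice does not affect the P values.

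**Formula.** With k = 3 methods and ties, Friedman's statistic is (k − 1) × Σⱼ(column sum of rank deviations)² ÷ Σ(all squared rank deviations), where deviations are taken from the mean rank of 2. It has 2 degrees of freedom, so P = exp(−χ²/2).

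If two methods agree and the third reads higher, the ranks are 3, 1.5, 1.5 and the deviations +1, −0.5, −0.5. If the third reads lower, the signs reverse. Each such tooth adds 1 + 0.25 + 0.25 = 1.5 to the denominator. With u teeth higher and v teeth lower:

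χ² = 2 × 1.5(u − v)² ÷ 1.5(u + v) = 2(u − v)²/(u + v)

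The squared difference removes the sign, so the P value carries no direction.

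**Scenarios** (readings as AI/CBCT/microscope; all other teeth read 3/3/3 or 4/4/4):

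| Case | Discordant teeth | Molars with 3 or 4 canals | χ² | P |
|---|---|---|---|---|
| a | 20 at 4/3/3 | 106/106/106 | 2·20²/20 = 40 | 2 × 10⁻⁹ |
| b | 20 at 3/4/4 | 106/106/106 | 40 | 2 × 10⁻⁹ |
| c | 20 at 4/4/3 | 106/106/106 | 40 | 2 × 10⁻⁹ |
| d | 10 at 3/2/2, 10 at 4/5/5 | 106/86/86 | 2·0²/20 = 0 | 1.0 |
| e | 7 at 4/3/3 | 106/106/106 | 2·7²/7 = 14 | 0.0009 |

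**What each case shows.**
- Cases a and b: the combined count is identical for all methods while Friedman's P is tiny. The P is the same whether AI reads the fourth canal that the others do not, or the reverse.
- Case c: AI and CBCT agree on every tooth, yet Friedman's test is highly significant. The paired contrasts separate this at once. AI versus CBCT has 0 discordant teeth. AI versus microscope has 20 in one direction, a difference of 20/106 = 18.9 percentage points in four-canal readings.
- Case d: the combined count favours AI by 20 teeth (Cochran's Q = 40, P = 2 × 10⁻⁹), and Friedman's test sees nothing.
- Case e: Friedman's test on canal number does register three-versus-four differences; seven such teeth suffice for P < 0.001.

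**Direction of the combined count.** Take 100 molars: 12 at 3/2/2, 38 at 3/3/3, 20 at 3/4/4 and 30 at 4/4/4. The combined count is 100 for AI against 88 for each comparator (exact McNemar P = 2 × 0.5¹² = 0.0005). Yet AI reads 70 × 3 + 30 × 4 = 330 canals, and each comparator reads 12 × 2 + 38 × 3 + 50 × 4 = 338. A higher combined count need not mean more canals.

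**The case against.** The strongest reply is that the combining occurs in one abstract sentence and not in the plan. Canal number was recorded, Friedman's test is specified on that number, and frequencies and percentages are planned. The phrase may simply summarise two rows of a frequency table. This stands: the documents do not settle it, and the plan defines no three-or-four outcome.

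Several stronger readings are tempting and are not supported:
- A reader might infer that a missed fourth canal is invisible to the analysis. It is hidden only in the quoted count; case e shows that Friedman's test responds to it.
- A reader might take it as established that P < 0.001 is Friedman's. It is a reasonable inference, since no other listed test compares canal number across the methods, but the abstract does not say so.
- A reader might infer that AI found fewer canals in this study, or that four read as three is the commonest error. The documents give no distribution of readings or errors, so neither can be said. The scenarios show what is possible, not what happened.
- A reader might want four or more versus three or fewer as the main contrast. That is another pooling. It would hide a five-canal tooth read as four, and would credit AI for reading four in a three-canal tooth.

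It is also fair to say that the objective concerns accuracy, which the abstract reports separately as 88.2%. That figure has no P value or comparator value beside it, and neither document defines a correct diagnosis, so it does not supply the missing pairwise evidence.

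None of this answers the remaining gap. Even if the phrase covers two separate rows, one P value from an unnamed test is attached to a claim about two comparators, and no pairwise test on canal number is listed.

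**Conclusion.** The concern holds in limited form. The plan as written cannot support a statement that AI differs significantly, and in its favour, from both CBCT and the microscope on canal readings. If the P value is Friedman's, it establishes at most that the three methods do not all rank alike. If it comes from some other test, that test is not in the plan and should be named.

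The size of any error in this trial cannot be computed without the paired counts. In principle the gap is wide: Friedman's P can be 2 × 10⁻⁹ with no AI–CBCT difference at all, and 1.0 with a 20-tooth difference in the combined count. The conclusion rests on reading the combined phrase literally and on inferring the source of the P value. The lack of a listed pairwise test depends on neither. This is a gap in analysis and reporting that is worth closing; it does not show that the claim is false.

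**What to change.** - Keep Friedman's test as the omnibus comparison. Add paired per-tooth comparisons of canal number for AI versus CBCT and AI versus microscope (for example, a sign or Wilcoxon signed-rank test). Give the paired difference with its 95% confidence interval, and state the multiplicity method (for example, Holm).
- Report the full distribution (2, 3, 4 and 5 canals) per method and the paired cross-tables, by treatment and molar type, with three and four canals in separate rows.
- Name the test beside each P value, and claim a pairwise difference only where that contrast was tested.
- Do not make four or more versus three or fewer the main contrast, and do not present a higher canal count as higher accuracy.

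The cost is a few tables and two paired comparisons per treatment group from data already recorded. The headline may weaken, for instance if the difference proves to lie mainly between the microscope and the two imaging-based readings.

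### The Conclusion singles out upper molars as where AI's advantage is greatest, but no reported result compares AI with CBCT or clinical examination by molar type

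*Protocol*

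**What the plan says.** The Protocol opens with a structured summary that already contains results. Its Conclusion ranks AI above CBCT and "clinical examination in both conventional and retreatment cases, particularly in upper molars".

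The Results in the same summary contain these relevant statements:

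- On tooth type: "There was no significant difference in AI accuracy between molar types", followed by "though the upper first molar had the highest accuracy (93.9" (a percentage, given without a denominator).
- On accuracy overall: "Overall, AI showed higher diagnostic accuracy (88.2%) compared to clinical examination and CBCT". No percentage is given for either comparator.
- On canal counts: "AI detected a significantly higher number of molars with three or four canals compared to clinical examination and CBCT". This carries P < 0.001 and is confined to conventional treatment cases. Retreatment cases are said to show a similar trend, with no P value.

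The Introduction states the aim of comparing the methods "in detecting root canals in upper first, upper second, and lower first molars", so there are two upper molar types and one lower.

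The Protocol's Statistical Analysis Plan section lists Friedman's "test for comparison between methods", kappa, and "ROC curve analysis to determine diagnostic accuracy measures (AUC comparison"). The SAP adds a logistic regression of correct versus incorrect diagnosis with molar type among its predictors, a ROC analysis of AI with CBCT as the point of reference, and a z-test between AUCs that it does not identify.

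**The concern.** In the Conclusion's sentence the upper-molar phrase qualifies a comparison between methods. Read as written, it says that AI's gain over CBCT and the microscope is greatest in upper molars. That is a subgroup claim about a difference between methods. Support for it would have to come from accuracy of each method within each molar type, or from a test of whether the difference between methods varies with molar type.

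The Results offer neither. Their one finding on tooth type concerns AI alone and is non-significant, and the Conclusion leaves that out. The conclusion is the part of a summary that most readers carry away, and this one could lead them to prefer AI to CBCT or the microscope in upper molars on the strength of a comparison that is not shown.

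**Working it through.** **Inputs**

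- Methods: three (AI, CBCT read by endodontists, clinical examination by microscope). Protocol, Methods.
- Molar types: three (upper first, upper second, lower first). Protocol, Introduction.
- AI accuracy: 88.2% overall, 93.9% in the upper first molar. Protocol, Results.
- Teeth: 212 molars, with no split by type. Protocol, Study Design.
- Significance level: 0.05, sidedness not stated. SAP.
- Not given: any accuracy for CBCT or clinical examination; AI accuracy in the upper second or lower first molar; a P value, interval or counts for the molar-type comparison.

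**1. What the phrase asserts.** Write A(m, t) for the accuracy of method m in molar type t, and D(m, t) = A(AI, t) - A(m, t) for AI's advantage over comparator m. The phrase says that D is larger in upper molars than in the lower first molar. A high A(AI, t) alone does not show this, because A(m, t) may be equally high in the same teeth.

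**2. What is available.**

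- Accuracies A(m, t): 3 × 3 = 9. Reported: 1 (AI, upper first, 93.9%). Missing: 8.
- Differences D(m, t): 2 × 3 = 6. Reported: 0.
- Overall accuracies: 1 of 3 methods (AI, 88.2%).

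No value of D can be calculated for any tooth type, or overall.

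**3. The only gap that can be calculated.** 93.9 - 88.2 = 5.7 percentage points. This is AI in one tooth type against AI in all teeth, upper first molars included. It is not a difference between methods.

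**4. Upper first is not all upper molars.** That the upper first molar ranks highest does not order the other two. On the reported text the upper second molar could be the least accurate of the three.

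**5. Planned analyses.**

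| Analysis | What it compares | Does it give D by molar type? |
|---|---|---|
| Friedman's test | number of canals found by the three methods | No: counts, not accuracy; molar type not named |
| Kappa | agreement between methods | No: molar type not named |
| Logistic regression | correct/incorrect diagnosis on five predictors (treatment, molar type, inter-orifice distance, percentage of canal unity, Vertucci class) | No: method is not a predictor, so there is no method-by-molar-type term |
| z-test on AUCs | not identified | Cannot be counted either way |

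**6. Is the reported non-significance credible?** Only the count 187/212 = 88.21% rounds to 88.2% with 212 teeth. Fixing that total and assuming the size of the upper-first group, I compared it with all other molars (Fisher's exact test, two-sided; approximate power at the 5% level):

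| Upper first (assumed) | Other molars | Fisher p | Power |
|---|---|---|---|
| 31/33 | 156/179 (87.2%) | 0.38 | 0.14 |
| 46/49 | 141/163 (86.5%) | 0.21 | 0.25 |
| 62/66 | 125/146 (85.6%) | 0.11 | 0.40 |
| 77/82 | 110/130 (84.6%) | 0.049 | 0.54 |
| 92/98 | 95/114 (83.3%) | 0.019 | 0.67 |

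The statement is plausible for a group of up to about 66. The true split is unknown and the actual test may have compared three groups, so this is a consistency check only. The argument does not depend on it.

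**7. A conditional point.** The SAP measures AI's accuracy with CBCT as the reference. If the 93.9% was obtained that way, A(CBCT, t) is 100% by construction and D(CBCT, upper first) = 93.9 - 100 = -6.1 points. Such a figure expresses agreement with CBCT and cannot show a gain over it in any tooth type.

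**The case against.** The strongest reply is that the phrase may be a loose echo of the Results sentence about AI's own accuracy, which does put an upper molar first. On that reading nothing is contradicted, and the fault is imprecise wording. This is a possible reading, but the grammar ties the phrase to superiority over the comparators. Even the looser reading stretches one figure for upper first molars to cover upper second molars as well.

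Second, non-significance is not equality. With the assumed group sizes of 33 to 82 above, power is only 0.14 to 0.54. That stands, and it is why the claim is called unsupported rather than false. Low power does not supply the missing evidence.

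Third, the SAP's silence on molar type does not prove that no such comparison was made. The SAP does not tie Friedman's test to treatment group either, yet the Results report a comparison of methods confined to conventional cases. That also stands: a molar-type comparison may have been run, but none is reported.

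Fourth, counting figures absent from a summary measures its level of detail, not the size of an error. This is fair as far as it goes. The count is used here only to show that nothing reported bears on the claim.

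Finally, the main hypothesis does not concern molar type, so the point leaves the study's principal comparison untouched. That limits its weight without removing the need to correct the sentence.

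**Conclusion.** The concern holds. The upper-molar emphasis is not supported by any result in the documents: none of the six differences it would rest on is reported, and the one related finding, on AI alone, was non-significant. It is not shown to be false, since the source is a summary and fuller results may exist.

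This conclusion rests on reading the phrase as part of the comparison between methods, and on the documents as supplied. It needs no assumption about group sizes, and it does not depend on CBCT having been the reference for the 93.9%. The sentence should be changed; the fault is in a secondary subgroup claim, not in the design or the planned analysis.

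**What to change.** Delete the last four words of the Conclusion's first sentence. Alternatively, replace them with a separate sentence: *AI accuracy did not differ significantly between molar types; it was numerically highest in upper first molars (93.9%).*

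Either change costs one phrase, needs no new data or analysis, and yields a somewhat less favourable conclusion.

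Keeping the claim is not an equally cheap alternative. It would need the accuracy of all three methods in each molar type, with counts and intervals, and a method-by-molar-type comparison, all judged against a reference standard independent of the methods compared. The documents do not clearly define such a standard, so it is not known whether the data already collected would be enough.

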# **Study Objectives and Hypotheses**

• **Objective**: To evaluate and compare the accuracy of AI, CBCT, and clinical examination in detecting the number of root canals in maxillary and mandibular molars.

• **Hypothesis**: AI will demonstrate superior diagnostic accuracy compared to CBCT and clinical examination.

## **Study Design**

- Sample Size: 212 molars.
- Randomization: Not applicable (observational study).
- **Blinding**: Independent assessment by two experienced endodontists for CBCT and clinical examination.
- Control Group: Not applicable.

# **Eligibility Criteria**

Inclusion Criteria:

- Male and female patients who were capable of providing informed consent.
- Age between 18 to 40 years old.
- A restorable tooth.

## Exclusion Criteria:

- Patients that underwent vital pulp therapies.
- Patients with calcifications in pulp space.
- Open apex/immature roots.
- Teeth restored by full coverage crowns.
- Pregnant women by taking adequate history from patient and pregnancy test that was done in the first visit

#### **Study Procedures**

- CBCT scans are analyzed by endodontists and AI software (Diagnocat).
- Clinical examination is performed using a dental operating microscope (DOM).
- The detected number of canals is recorded and compared across methods.
- Statistical analysis is performed to evaluate accuracy.

#### **Statistical Analysis Plan**

- Descriptive analysis of frequencies and percentages.
- Friedman's test for comparison between methods.
- Kappa statistics for agreement between methods.
- ROC curve analysis to determine diagnostic accuracy measures (AUC comparison).

## **Risks and Benefits**

- Risks:
  - Radiation exposure from CBCT scans.
  - Potential diagnostic errors leading to treatment challenges.
  - Procedural complications, such as tool breakage or nerve injury.
- Benefits:
  - Enhanced diagnostic accuracy and reduced diagnostic errors.
  - Improved treatment outcomes and reduced human error.

